8.1.1 Discontinuation of Study Intervention

8.1.1. Tier 1 Stopping Rule:

The primary objective of Tier 1 is to assess the feasibility of protocol therapy in subjects with advanced MPNs as measured by the incidence of dose limiting toxicity (DLT, see *Definition of Dose Limiting Toxicity* section). Toxicities are assessed by CTCAEv5 criteria. Up to a total of 12 patients will be accrued to Tier 1. Tier 1 will be stopped for safety considerations under the following conditions:

- Any patient has grade 5 (lethal) DLT occurring within the first 12 weeks of starting vactosertib; or
- More than two patients experience a dose-limiting toxicity (DLT) at any dose, within the first 12 weeks on study.

Trial accrual will be suspended and a DSMB convened if either of these *Tier 1 Stopping Rule* criterion is triggered. If more than two patients have a DLT at the same dose level, then further accrual to that dose level and higher dose levels will be suspended. Pending review with DSMB, the study may be re-opened with amendment reflecting changes to the permitted dose levels. A planned stop to Tier 1 accrual will occur after 12 subjects have received at least one dose of vactosertib. At this time, the DSMB will be convened if fewer than 1 of the first 12 patients experience clinical benefit.

Protocol therapy will be considered safe if the *Tier 1 Stopping Rule* is not triggered. The following table provides the marginal probability of declaring the intervention unsafe for different rates of severe toxicity (as defined by *Tier 2 Stopping Rule*). This *Tier 1 Stopping Rule* protects against an unexpectedly high rate of severe toxicity.

Tier 1	True Rate of Severe Toxicity				
	5%	10%	15%	20%	30%
Probability of Declaring Unsafe	12%	35%	56%	73%	91%

If the Tier 1 safety boundaries are not crossed, this treatment strategy will be considered safe for expansion to Tier 2. Feasibility and toxicity will continue to be monitored in the Tier 2 portion of the study. A total of 37 patients will be accrued (Tier 1 + Tier 2) and the Tier 2 rule stopping rule applies to all subjects (up to 37) enrolled.

8.1.2. Tier 2 Stopping Rule:

- Any patient has grade 5 (lethal) DLT occurring within the first 12 weeks of starting vactosertib; or

- More than five patients experience a dose-limiting toxicity (DLT) at any dose, within the first 12 weeks on study.

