12.1 Study Design/Endpoints

12.1.1. Optimal Two-Stage Design, and Criteria to Proceed to Tier 2:

A Simon Two-stage Optimum Design was used to minimize the number of subjects exposed to vactosertib if it is found to be an unsuitable agent for the treatment of anemic patients with Ph-neg MPNs. Further development of vactosertib would be warranted if $\geq 20\%$ of subjects met *Criteria for Clinical Benefit* ([section 10.1](#)) without dose-limiting toxicity (see *Definition of Dose Limiting Toxicity* section). The study will be terminated early if fewer than 1 subject treated in the first tier (up to 12 subjects) meet these criteria. Using these criteria, there is less than a 10% chance of inappropriately accepting (α , type 1 error) vactosertib if it is not truly useful. Conversely, there is less than a 10% chance of inappropriately rejecting (β , type 2 error) vactosertib if it is actually a useful drug for anemic patients with Ph-neg MPNs.

Table 4: Optimal Two Stage Design

Response Probability Indicating Unacceptably Low vactosertib Activity	0.05
Response Probability Indicating Substantial vactosertib Activity	0.20
Probability of Accepting Poor Drug	0.1
Probability of Rejecting Good Drug	0.1
Number of Tier 1 Subjects	12
Number of Tier 1 Responders to Advance to Tier 2	≥ 1
Maximal Number of Subjects	37
Number of Tier 2 Responders to Advance Development	≥ 4

The Simon Two-stage Optimum Design is expected to minimize the number of subjects exposed to vactosertib if it is found to be an unsuitable agent for the treatment of anemic patients with Ph-neg MPNs (see *Criteria for Decision to Proceed to Tier 2* section). If 1 or more subjects meets the *Composite Response & Toxicity Endpoint* ([Table 5](#)) then the study will proceed to Tier 2 and another 25 subjects will be enrolled. After completion of Tier 2, if four or more subjects meet the *Composite Response & Toxicity Endpoint* then vactosertib

will have shown preliminary efficacy and feasibility to justify further evaluation as an agent to treat anemic patients with Ph-Neg MPNs.

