12.2 Sample Size/Accrual Rate

Total sample size of the study is 37 patients, 12 for Tier 1 and 25 for Tier 2. The number of potentially eligible subjects seen at our institution is on average 10 per month based on an i2b2 database query. The projected accrual rate to the study is estimated to be 2 patients per month.

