The principal investigator will be primarily responsible for monitoring the safety of the study, adverse events, both serious and non-serious and deaths that occur during study participation by subjects. All adverse events will be monitored until they resolve or are clearly determined to be due to a subject's disease or intercurrent illness(es).

At the completion of Tier 1, all data necessary to evaluate [Criteria for Decision to Proceed to Tier 2](#) section) will be reported to WCM Statistician, WCM DSMB and Medpacto. The Simon Two-stage

Optimum Design is expected to minimize the number of subjects exposed to vactosertib if it is found to be an unsuitable agent for the treatment of anemic patients with Ph-neg MPNs. If 1 or more subjects meets the endpoint then the study will proceed to Tier 2 and another 25 subjects will be enrolled). This decision will be submitted to WCM IRB at the time of continuing review.

After completion of Tier 2, all data necessary to evaluate will be reported to WCM Statistician, WCM DSMB and Medpacto. If four or more subjects meet the Composite Response & Toxicity Endpoint then vactosertib will have shown preliminary efficacy and feasibility to justify further evaluation as an agent to treat anemic patients with Ph-Neg MPNs. This interpretation will be submitted to WCM IRB at the time of continuing review.

Should the Stopping Rules for [Tier 1](#) or for [Tier 2](#) be met, accrual of new subjects will be immediately suspended and the WCM IRB and Medpacto will be notified. The study DSMB will meet to review study data. The DSMB may either recommend permanent closure of the study or may allow protocol revision/amendment and submission to WCM IRB for review. DSMB recommendations will be submitted to Medpacto and WCM IRB.

All protocol amendments and consent form modifications will be made by the Principal Investigator. Medpacto will have the opportunity to review and approve the changes prior to submission of these changes to the local IRB.

[Section 7.9, Criteria for Removal from Study](#), details treatment stopping rules for individual patients.

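### Section 12.1.1's stated chance of under 10% of rejecting a useful drug describes the efficacy cut-offs alone; with the DLT stopping rules as worded, the chance of advancing without a safety stop is 88/72/43/18% at DLT rates of 5/10/15/20%

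*Combined protocol and SAP*

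**What the plan says.** Section 12.1.1 describes a Simon optimal two-stage design. Table 4 sets the two hypotheses as "Response Probability Indicating Unacceptably Low vactosertib Activity 0.05" and "Response Probability Indicating Substantial vactosertib Activity 0.20". A response here is the composite of Table 5: clinical benefit held for at least 8 weeks with no DLT. At least 1 responder among the 12 Tier 1 patients opens Tier 2, and at least 4 among all 37 justify further development. The section then states that "there is less than a 10% chance of inappropriately accepting" a poor drug, and "Conversely, there is less than a 10% chance of inappropriately rejecting" a useful one.

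Section 8.1 adds safety rules that run in parallel. Tier 1 stops if "More than two patients experience a dose-limiting toxicity (DLT) at any dose, within the first 12 weeks on study". The Tier 2 rule, which 8.1.1 applies to all patients in both tiers (up to 37), is triggered if "More than five patients experience a dose-limiting toxicity (DLT) at any dose, within the first 12 weeks on study". Either tier also stops on any lethal DLT within 12 weeks. Under 8.1.1, treatment is regarded as safe to expand when the Tier 1 boundaries are not crossed. Section 15 says that if a stopping rule is met, "accrual of new subjects will be immediately suspended" and the DSMB reviews; it may recommend closure or allow a revised protocol. Section 8.1 tabulates the chance of a safety stop for true toxicity rates of 5% to 30%, apart from any efficacy calculation.

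**The concern.** To advance, the trial must meet the response cut-offs and also stay within the DLT limits. Section 12.1.1 computes its error rates from the response cut-offs only, and does not say so. Because usefulness is defined there as benefit without DLT, a reader can reasonably take the 10% figure to cover tolerability as well. The efficacy-only beta of 9.8% leaves only 0.2 percentage points before the promise is broken.

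At stake is how the DSMB, the IRB and the investigators read a trial suspended for DLTs. They would set it against a risk of missing a useful drug that the full set of rules does not deliver.

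**Working it through.** **Inputs from the documents.** Null and target response rates 0.05 and 0.20 (Table 4). Stages 12 and 25, total 37 (12.2). Efficacy cut-offs at least 1 of 12 and at least 4 of 37 (Table 4). DLT limits: no more than 2 of 12 and no more than 5 of 37 (8.1.1, 8.1.2 as worded). Responder and DLT are mutually exclusive (Table 5).

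**Assumptions.** The plan names no expected DLT rate, so d takes the values 5, 10, 15 and 20% from the grid in 8.1. One rate d serves both the 12-week stopping rules and the no-DLT condition of the composite, which has no such time limit. The lethal-DLT limb is left out because no rate is given; including it could only lower the results.

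**Step 1: the plan's own figure.**

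P(advance) = Σ over x ≥ 1 of P(Bin(12, p) = x) × P(Bin(25, p) ≥ 4 − x).

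At p = 0.20:
- x = 1: 0.2062 × 0.9018 = 0.1859
- x = 2: 0.2835 × 0.9726 = 0.2757
- x = 3: 0.2362 × 0.9962 = 0.2353
- x ≥ 4: 0.2054

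The sum is 0.9024 before rounding of the terms, so beta = 0.0976. At p = 0.05 the same sum is 0.0935. Both are below 10%, and a search over designs returns 0/12, 3/37 as the Simon optimum (expected size 23.5 under the null). The plan's figure reproduces for the efficacy cut-offs.

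**Step 2: add the DLT rules as worded.** Each patient is a responder without DLT (0.20), has a DLT (d), or neither (0.80 − d). With R for responders and D for DLTs, sum the exact trinomial probabilities over R₁ ≥ 1 and D₁ ≤ 2 in the first 12, with R ≥ 4 and D ≤ 5 in all 37.

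| True DLT rate | Advances without a safety stop | Does not |
|---|---|---|
| 0% | 90.2% | 9.8% |
| 5% | 88.0% | 12.0% |
| 10% | 71.9% | 28.1% |
| 15% | 42.8% | 57.2% |
| 20% | 18.4% | 81.6% |

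At 2% and 3% the chance of advancing is 90.1% and 89.8%, so the 10% line is crossed between them. As a rough check, treat the two rules as independent. The DLT rules alone are not triggered with probability 97.4, 78.8, 46.3 and 19.5%; multiplying by 0.9024 gives 87.9, 71.1, 41.7 and 17.6%.

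**Step 3: sensitivity (advances without a stop, DLT 5/10/15/20%).**
- 20% read as the benefit rate before patients with a DLT are removed, so the composite rate is 0.20 × (1 − d): 86/69/40/17%.
- Limit of five counted in the 25 Tier 2 patients only, against the wording of 8.1.1: 88/78/57/32%.
- Cut-offs of at least 2 of 12 and at least 5 of 37: 79/50/22/7%.

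The chance of not advancing exceeds 10% in every variant at all four rates.

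**Step 4: why the last variant matters.** The tables printed in 8.1 do not follow the worded cut-offs.

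| DLT rate | Tier 1 printed | ≥2 of 12 | >2 of 12 | Tier 2 printed | ≥5 of 37 | >5 of 37 |
|---|---|---|---|---|---|---|
| 5% | 12% | 11.8% | 2.0% | 3.1% | 3.6% | 1.0% |
| 10% | 35% | 34.1% | 11.1% | 31% | 31.0% | 16.0% |
| 15% | 56% | 55.7% | 26.4% | 67% | 67.0% | 48.7% |
| 20% | 73% | 72.5% | 44.2% | 89% | 88.8% | 77.8% |

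The printed values lie close to the one-lower cut-offs. A joint row on the worded rule would also clash with them: at 10%, a 35% Tier 1 stop caps advancement at 65%, below 71.9%.

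**The case against.** **The arithmetic is not wrong.** The error statement refers to the criteria just listed, the response cut-offs, and for those it is correct. This stands: the defect is an unlabelled scope and a missing joint figure.

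**The safety stop is disclosed.** Section 8.1 prints its probability over a 5–30% grid. True, but never jointly with efficacy, and on cut-offs that differ from the worded rule.

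**A safety stop is not a type II error.** A reader might infer from the table that the type II error is 12% to 82%. The documents do not support that. Section 8.1.1 presents the rule as protection against unexpectedly high toxicity, and no acceptable DLT rate is named. At 15–20% a stop may be the right decision, so it cannot be counted as inappropriate rejection.

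**A stop is not the end of the trial.** A reader might also take 88/72/43/18% as the overall chance of advancing. Sections 8.1.1, 12.5 and 15 let the DSMB permit continuation or re-opening. No probability of that is given, so an overall chance cannot be computed.

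**The power is not lost unless DLTs are virtually absent.** It would be too strong to say that it is: at a 5% rate it is 88% against 90%. Section 13.1.1 expects drug-related grade 3 or 4 events to be rare. It also reports grade 3 or 4 events from any cause in 22 of 60 monotherapy patients. These are not DLT counts, so neither statement fixes the rate.

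**Conclusion.** The point holds as one of labelling and completeness. The stated bound on missing a useful drug belongs to the efficacy boundaries, and the plan does not say that it ignores the DLT rules. With those rules as worded, the chance of advancing without a safety stop at the 20% target is 88/72/43/18% at DLT rates of 5/10/15/20%: 2 percentage points below the efficacy-only 90% at a 5% rate, and 18 points below it at 10%. The result rests on a single DLT rate for both definitions, the cumulative count over 37 patients, and omission of the lethal-DLT limb. The exact values depend on which DLT cut-offs are meant, which 8.1 leaves unsettled.

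The stated type I error bound is not threatened. Adding a safety requirement can only lower the chance of advancing a poor drug below 9.3%.

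**What to change.** 1. In 12.1.1 and Table 4, state that alpha 9.3% and beta 9.8% are properties of the efficacy boundaries only and ignore the safety stopping rules. Do not describe them as conditional on no safety stop, which would be false. Responders and DLTs exclude each other, so conditioning changes both: at DLT rates of 5/10/15/20% the conditional beta is 9.6/8.8/7.4/5.9% and the conditional alpha 9.4/9.9/10.9/12.4%.
2. Reconcile the worded DLT cut-offs in 8.1.1 and 8.1.2 with the probability tables printed there. Which is intended is for the sponsor and investigator to settle.
3. Then print beside Table 4 the joint probability of advancing without a safety stop under the reconciled rule: 88/72/43/18% as worded, or 79/50/22/7% under the cut-offs that the tables imply. State the assumptions, and note that the DSMB may re-open the study.

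The cost is a sentence, a small table and the reconciliation of 8.1, which has to come first. No efficacy boundary or sample size changes. The downside is a less favourable stated power.

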12.2.2 Composite response/ Toxicity measure

Responding subjects will have met *Criteria for Clinical Benefit* ([section 9.1](#)) for at least 8 weeks. This will ensure that a stable vactosertib dosing schedule can be achieved. Responding subjects will not experience dose limiting toxicity (see *Definition of Dose Limiting Toxicity*). Only subjects meeting all criteria will be considered responders.

Table 5: Composite Response & Toxicity Endpoint

Adequate Response	Meets Criteria for Clinical Benefit
Stable Response	Meets Criteria for Clinical Benefit to vactosertib for \geq 8 weeks
Tolerable	No Dose Limiting Toxicity Experienced

12.2 Sample Size/Accrual Rate

Total sample size of the study is 37 patients, 12 for Tier 1 and 25 for Tier 2. The number of potentially eligible subjects seen at our institution is on average 10 per month based on an i2b2 database query. The projected accrual rate to the study is estimated to be 2 patients per month.

12.3 Stratification Factors

The study is not powered for statistical analysis of subgroups. Relevant factors that will be collected include MPN diagnosis, MPN duration and driver mutation, demographic variables such as subject age and gender. Monitoring and efficacy determination will be done for the entire population without stratification.

12.4 Analysis of Endpoints

12.4.1 Analysis of Primary Endpoints

Please see Table 4 and Section 12.1 for the detailed analysis of the Primary Endpoints.

12.4.2 Analysis of Secondary Endpoints

Clinical response to vactosertib will be assessed using the *Criteria for Clinical Benefit* outlined above as a composite endpoint. Patients achieving any of these criterial will be considered to have achieved clinical benefit. This endpoint will be used to define a preliminary estimate of the potential efficacy of vactosertib in the study population. Complete enrollment to both tiers (37 total) will allow us to confidently identify a *Clinical Benefit* response rate of more than 30%. This estimate has a significance of ≤ 0.1 and a power of 0.8 and is based upon a reported clinical improvement rate of $\leq 10\%$ (almost

entirely due to symptomatic response) in similar patient populations with best available therapy^{34,35}. Reported rates of splenic and/or erythropoietic responses to best available therapy are $\leq 3\%$. The 37 subjects enrolled on this study will allow Splenic Response and Erythropoietic Response rates of at least 20% to be individually tested with a power of 80% and a significance of $< 0.1\%$. If after complete accrual of 37 subjects, more than 11 patients meet criteria for Composite Response, or more than 7 patients meet criteria for Splenic or Erythropoietic Response, vactosertib will be considered to have sufficient efficacy for definitive testing in a randomized study.

The secondary endpoints of erythropoietic (HGB and RBC transfusion), symptomatic, and splenic responses will be directly tested as described in the preceding section. While limited by the small sample size, additional endpoints will be assessed including molecular (MPN driver variant allele frequency), pharmacodynamic (SMAD2/3 phosphorylation in bone marrow and/or blood CD34+ hematopoietic stem and progenitor cells), and histologic (bone marrow cellularity and fibrosis score) responses. The incidence of hematologic toxicities, infections, disease progression, thrombosis events, and the probability of overall and progression free survival, will be monitored. Secondary endpoints will be reported using descriptive statistics but no formal hypothesis testing will be performed.

Other secondary endpoints will be reported using descriptive statistics but no formal hypothesis testing will be performed. The following endpoints will be analyzed:

12.4.2.1 Histologic response defined by any reduction in grade of bone marrow fibrosis by histopathologic assessment at 16 weeks.

12.4.2.2 Molecular response defined by a decrease in allelic ratio of MPN-driver mutations (eg. JAK2, CALR, and MPL allelic ratio) in blood and/or bone marrow cells.

12.4.2.3 Pharmacodynamic Response defined as any of the following:

- Reduced immunohistochemical staining for SMAD2/3 phosphorylation in bone marrow biopsy sections (See Figure 1).
- Reduced mean fluorescence intensity of SMAD2/3 phosphorylation staining in peripheral blood hematopoietic stem and progenitor cells (HSPCs) or mature progeny as assessed by flow cytometry (See Figure 2).
- Reduced mean fluorescence intensity of SMAD2/3 phosphorylation staining in bone marrow hematopoietic stem and progenitor cells (HSPCs) or mature progeny as assessed by flow cytometry.

12.4.2.4 ToxicityThe incidence of hematologic toxicities, infections, disease progression, thrombosis events, and the probability of overall and progression free survival, will be monitored.

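### Section 12.4.2: the cut-offs of more than 11 and more than 7 of 37 give 43% and 47% power per test, not the stated 80%, and no cut-off at 37 patients meets both 80% power and the printed significance of <0.1%

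*Combined protocol and SAP*

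**What the plan says.** Section 12.4.2 makes two power claims for the full 37 patients.

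- **Clinical Benefit.** A rate above 30% can be identified with significance ≤0.1 "and a power of 0.8 and is based upon a reported clinical improvement rate of" ≤10%.
- **Splenic and erythropoietic response.** The background is put at ≤3%. The 37 subjects are said to allow "Splenic Response and Erythropoietic Response rates of at least 20% to be individually tested with a power of 80" per cent, with the significance printed as <0.1%.

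One decision rule follows. If "more than 11 patients meet criteria for Composite Response, or more than 7 patients meet criteria for Splenic or Erythropoietic Response", then "vactosertib will be considered to have sufficient efficacy for definitive testing in a randomized study". No other critical value is given for these tests.

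The section opens by describing Clinical Benefit as "outlined above as a composite endpoint". It does not define Composite Response. Section 12.2.2 (Table 5) defines a stricter Composite Response & Toxicity Endpoint, which needs benefit for at least 8 weeks and no dose-limiting toxicity: "Only subjects meeting all criteria will be considered responders".

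Section 12.4.2 also says that the erythropoietic, symptomatic and splenic responses "will be directly tested as described in the preceding section", and later in the same paragraph that "Secondary endpoints will be reported using descriptive statistics but no formal hypothesis testing will be performed".

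**The concern.** The two cut-offs look like expected counts rather than critical values: 0.30 × 37 = 11.1 and 0.20 × 37 = 7.4. A threshold set at the expected count under the target rate is passed about half the time when the target is true, whatever power is quoted beside it.

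This is the only rule in the plan that says when the drug should go to a randomized study. A reader would take each test to have 80% power. If it does not, a drug that truly meets one target would more often than not be judged insufficient, and the plan would not have disclosed that risk.

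**Working it through.** **Inputs** (12.4.2): n = 37; Clinical Benefit 30% against 10%, significance ≤0.1, power 0.8; splenic and erythropoietic response each 20% against 3%, significance <0.1%, power 80%; cut-offs more than 11 (12 or more) and more than 7 (8 or more).

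**Formula.** For a rule of r or more responders,

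P(X ≥ r | p) = Σ C(37, k) p^k (1 − p)^(37 − k), summed over k = r to 37.

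Alpha uses the background rate and power uses the target rate.

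**Clinical Benefit, 30% against 10%**

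| Cut-off | Alpha at 10% | Power at 30% |
|---|---|---|
| ≥7 | 7.1% | 95.6% |
| ≥8 | 2.7% | 90.5% |
| ≥9 | 0.9% | 82.4% |
| ≥10 | 0.3% | 71.1% |
| ≥11 | 0.07% | 57.6% |
| ≥12 (plan's rule) | 0.02% | 43.4% |

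The claim for 37 patients can be met, by cut-offs of 7, 8 or 9. It is not met by the cut-off in the plan, which reaches 80% power only at a true rate of about 38%.

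**Splenic or erythropoietic response, each 20% against 3%**

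| Cut-off | Alpha at 3% | Power at 20% |
|---|---|---|
| ≥3 | 9.9% | 98.7% |
| ≥4 | 2.4% | 95.5% |
| ≥5 | 0.48% | 88.8% |
| ≥6 | 0.076% | 77.8% |
| ≥7 | 0.010% | 63.0% |
| ≥8 (plan's rule) | 0.001% | 46.7% |

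The plan's cut-off reaches 80% power only at a true rate of about 26%. With significance <0.1% taken literally, 5 or more fails on alpha and 6 or more falls 2.2 points short on power, so no cut-off satisfies both. If 0.1 was meant, as for Clinical Benefit, then 3, 4 or 5 or more all qualify; 8 or more still has 46.7% power.

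**Reading the cut-offs generously**, as 11 or more and 7 or more, power is 57.6% and 63.0%.

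**The whole rule.** The plan gives no overlap between responses, so those below are assumptions. One million multinomial trials per row.

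| True rates (assumed) | Splenic and erythropoietic counted separately | Patients with either response counted |
|---|---|---|
| Symptom-only benefit 30% | 43% | 43% |
| Erythropoietic 20% only | 47% | 47% |
| Erythropoietic 20% plus symptom-only 10% (benefit 30%) | 56% | 56% |
| Splenic 20%, erythropoietic 20%, both 10% (benefit 30%) | 66% | 91% |
| Splenic and erythropoietic 20% each, independent (benefit 36%) | 79% | 98% |
| Splenic and erythropoietic 20% each, no overlap (benefit 40%) | 89% | 99% |

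**If Composite Response means the Table 5 endpoint**, 43% is a ceiling at 30% Clinical Benefit. If 90% or 80% of responders keep the benefit for 8 weeks without dose-limiting toxicity (assumed), the rate is 0.30 × 0.9 = 27% or 0.30 × 0.8 = 24%, and P(X ≥ 12) is 28% or 16%.

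**Primary rule, for comparison.** Table 4 (at least 1 of 12, then at least 4 of 37; 5% against 20%) reproduces: alpha 9.3% and power 90.2%, against the stated limit of 10% on each error.

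**The case against.** The best defence is that the 80% describes what 37 patients can support, while the cut-offs are a separate and deliberately strict bar on the observed rate: 12/37 = 32% and 8/37 = 22%, just above the two targets. A strict bar is legitimate, and for Clinical Benefit the statement about sample size is correct. But the plan does not say the bar is meant to be strict, and it gives no other rule, so the stated power does not describe the decision that will be made.

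Other points carry weight.

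- The printed <0.1% may be a misprint for 0.1, and read literally the failure is narrow (77.8% against 80%). That part is as much a request for clarification as an error. It does not rescue the cut-off of more than 7.
- If more than 7 counts patients with either response, the whole rule has 91% to 99% power in the scenarios where both rates are 20%. The text does not say which count applies, and it describes the two responses as tested individually.
- Composite Response most naturally refers back to the Clinical Benefit composite in the same section, so the 28% and 16% figures apply only on the other reading and rest on assumed retention.
- The sentence ruling out formal testing may be a leftover, since the next paragraph repeats it for the other secondary endpoints. It still contradicts the text as it stands.
- Table 4 also governs advancing development and is sound. Section 12.4.2 drives no dosing, stopping or enrolment decision.

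**Conclusion.** The concern holds. Per test, the cut-offs deliver 43% and 47% power where 80% is stated, with alphas of 0.02% and 0.001%. These figures are exact and need only the plan's own rates, cut-offs and n = 37. For 20% against 3%, the printed significance and the stated power cannot both be met at 37 patients.

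The power of the whole rule ranges from 43% to 99% across the scenarios tried, depending on overlaps the plan does not state and on how the more-than-7 count is read. The sample size is adequate for Clinical Benefit, and for the other two responses if significance 0.1 was meant. The primary analysis in 12.1.1 is unaffected. This should be fixed, because a prespecified go rule does not have the power stated beside it.

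**What to change.** Keep 37 patients and choose one of two routes.

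- **(a) Keep the cut-offs.** State power of 43% and 47% with alphas of 0.02% and 0.001%, and describe the bar as deliberately strict.
- **(b) Reset the cut-offs.** For Clinical Benefit use 7, 8 or 9 or more (9 or more: alpha 0.9%, power 82%). For splenic and erythropoietic response use 5 or more with alpha restated as 0.5% (power 89%), or 6 or more with power restated as 78%. If 0.1 was the intended significance, 5 or more meets both stated figures as it is.

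Whichever is chosen:

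- State whether <0.1% means 0.1% or 0.1.
- State whether more than 7 counts each response separately or patients with either, and give the power of the whole rule under stated overlaps.
- Define Composite Response in relation to the Table 5 endpoint.
- State how this rule relates to the 4-of-37 rule in 12.1.1: one leads to a randomized study, the other to further evaluation.
- Remove whichever of the two statements on formal testing does not apply.
- Give the splenic denominator. Section 10.1.2 makes patients with a baseline spleen less than 5 cm below the costal margin ineligible for splenic response, and 12.6.2 assesses response after at least 4 cycles. With 30 or 25 eligible patients (assumed), P(X ≥ 5 | 20%) is 74.5% or 58%, not 89%.

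The cost is protocol wording, with no added patients. Under route (a) the stated power becomes less favourable.
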